7.12 Secondary Endpoints - Critical-Care Pain Observation Tool (CPOT)

7.12.1 Definition

Critical-Care Pain Observation Tool (CPOT) total score will be calculated from each individual item along with absolute and percent change.

Indicator	Score	Description
Facial expression 
[name], B.Sc., PhD(student) School of Nursing, McGill University
	Relaxed, neutral	0 No muscle tension observed
	Tense	1 Presence of frowning, brow lowering, orbit tightening and levator contraction or any other change (e.g. opening eyes or tearing during nociceptive procedures)
	Grimacing	2 All previous facial movements plus eyelid tightly closed (the patient may present with mouth open or biting the endotracheal tube)
Body movements	Absence of movements or normal position	0 Does not move at all (doesn't necessarily mean absence of pain) or normal position (movements not aimed toward the pain site or not made for the purpose of protection)
	Protection	1 Slow, cautious movements, touching or rubbing the pain site, seeking attention through movements
	Restlessness/Agitation	2 Pulling tube, attempting to sit up, moving limbs/thrashing, not following commands, striking at staff, trying to climb out of bed
Compliance with the ventilator (intubated patients) OR Vocalization (extubated patients)	Tolerating ventilator or movement	0 Alarms not activated, easy ventilation
	Coughing but tolerating	1 Coughing, alarms may be activated but stop spontaneously
	Fighting ventilator	2 Asynchrony: blocking ventilation, alarms frequently activated
	Talking in normal tone or no sound	0 Talking in normal tone or no sound
	Sighing, moaning	1 Sighing, moaning
	Crying out, sobbing	2 Crying out, sobbing
Muscle tension Evaluation by passive flexion and extension of upper limbs when patient is at rest or evaluation when patient is being turned	Relaxed	0 No resistance to passive movements
	Tense, rigid	1 Resistance to passive movements
	Very tense or rigid	2 Strong resistance to passive movements or incapacity to complete them
TOTAL		___ / 8

7.12.2 Analysis

No statistical tests will be performed.

7.12.3 Presentation

The CPOT will be presented using summary statistics with graphs over time presenting the mean, absolute and percent change.

7.13 Secondary Endpoints - Overall Survival

7.13.1 Definition

Overall Survival will be defined as 90 days survival. If a patient is alive at day 90 such patient will be censored. The overall survival time will be the time from randomization to either death or censored date (could be lost to follow up or day 90).

The incidence of death will be calculated.

7.13.2 Analysis

No statistical tests will be performed.

7.13.3 Presentation

The incidence of death will be presented using listings.

7.14 Secondary Endpoints – Hospitalization days

7.14.1 Definition

Total time in hospital is defined as (datetime of discharge from hospital – datetime of randomization). The time in intensive care unit will be calculated as time of first ICU visit until discharge from ICU unit. If no endpoint is recorded, time in hospital/ICU will be set to 30 days. If the patient died in hospital/ICU, the date of death (time 00:00 imputed if missing) will be used to calculate time in hospital/ICU.

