### 5.2 Discharge Criteria

The patient randomized to receive CM4620-IE should remain in the hospital until all 4 doses of CM4620-IE have been administered, and a CECT of the pancreas has been performed. The suggested criteria for discharging patients from the hospital are:

- Abdominal pain has resolved
- Normal oral diet is tolerated
- There is no clinical or laboratory evidence of an infection

If the patient is ready to be discharged before all 4 doses of CM4620-IE have been administered or the CECT of the pancreas has been performed, the PI or treating physician should contact the Medical Monitor prior to discharging the patient.

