**All patients will undergo a CECT of the pancreas on Day 5.**

- The CECT will be performed on Days 6 or 7 if unable to be performed on Day 5
- If the PI wishes to discharge a patient randomized to supportive care only before Day 5, a CECT should be performed prior to discharge
- If the PI wishes to delay the CECT beyond Day 7, the Medical Monitor should be contacted

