3.1.4 Secondary endpoints

The secondary efficacy endpoints are:

- CTSI Score categorized into Mild, Moderate and Severe
- Balthazar score
- Pancreatic Parenchymal Necrosis
 - < 30%
 - 30-50%
 - > 50%
- PASS score
- Tolerating Solid Food
 - Time to tolerating solid food
 - Arithmetic mean of time to tolerate 50% solid food
- Biomarker measurements including, but not limited to:
 - ANC/ALC (Absolute neutrophils count / Absolute Lymphocytes count)
 - C-Reactive Protein (CRP)
 - D-Dimer

- Procalcitonin
- IL-6
- IL-8
- SIRS
 - Time to resolution of SIRS
 - The number of days alive and free from SIRS
 - Total SIRS score
- Any Organ Failure (LISTINGS)
- Respiratory Failure (LISTINGS)
- Renal Failure (LISTINGS)
- Cardiovascular Failure (LISTINGS)
- Sequential Organ Failure Assessment (SOFA):
 - Respiration Score
 - Coagulation Score
 - Liver Score
 - Cardiovascular Score
 - Central Nervous System Score
 - Renal Score
 - SOFA total Score
- Modified Sequential Organ Failure Assessment (MSOFA):
 - Modified total SOFA Score
- Severity as defined by Revised Atlantic Classification of Acute Pancreatitis
- Severity as defined by Determinant Based Classification of Acute Pancreatitis
- APACHE II score
- Pain Numeric Rating Scale (PNRS) score
- Critical-Care Pain Observation Tool (CPOT) score
- Overall Survival (Listings)
- Number of hospitalized days
 - Total Days
 - Days in Intensive Care

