7.14.3 Presentation

Both the total number of hospital days and number of days at ICU will be presented using summary statistics.

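### Total hospital days compares drug with supportive care, but only the drug arm is asked to stay for four doses, a soft minimum of about 3.2 days that biases the comparison against the drug

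*SAP*

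**What the plan says.** SAP 3.1.4 places "Number of hospitalized days", split into total days and days in intensive care, in the list that opens "The secondary efficacy endpoints are". SAP 7.14.1 defines the total: "Total time in hospital is defined as (datetime of discharge from hospital – datetime of randomization". The formula is the same in both arms and makes no allowance for time spent in hospital because of the protocol. SAP 7.14.3 then says: "Both the total number of hospital days and number of days at ICU will be presented using summary statistics". Section 7 presents all parameters by treatment, and 7.14.2 rules out a test.

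The discharge rules differ by arm. Protocol 5.2: "The patient randomized to receive CM4620-IE should remain in the hospital until all 4 doses of CM4620-IE have been administered", with the addition "and a CECT of the pancreas has been performed". If a patient is ready before the doses or the scan are complete, "the PI or treating physician should contact the Medical Monitor prior to discharging the patient". For the other arm, protocol 8.6 (Day 5) says: "If the PI wishes to discharge a patient randomized to supportive care only before Day 5, a CECT should be performed prior to discharge".

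Neither document connects these rules with the endpoint, and SAP section 8, on changes from the protocol, is empty.

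**The concern.** For a supportive-care patient, time from randomization to discharge reflects recovery and local practice. For a drug patient who recovers quickly, it reflects the infusion schedule. If recovery were identical in the two arms, the drug arm would still show the longer mean stay. If the drug shortened recovery, the gain would be hidden in the patients who responded fastest, because they are the ones asked to wait.

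Short stays cannot be dismissed. Protocol 1.1 describes most acute pancreatitis as mild and self-limiting, entry excludes pancreatic necrosis, and the discharge rules themselves foresee readiness before the fourth dose and supportive-care discharge before Day 5. On the other side, entry requires SIRS or hypoxemia, which may lengthen stays. A reader who sees the two arm means side by side has nothing in the SAP to warn that they do not measure the same thing.

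**Working it through.** **Arm sizes.** The plan gives no length-of-stay figure to reproduce. The cohorts sum to 4 + 4 + 8 + 8 = 24, which at 3:1 is 18 drug and 6 supportive care.

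**Minimum stay from the schedule.**
- The fourth dose starts 72 h (±1 h) after the start of the first (protocol 8.5) and runs 4 h (7.4): 72 + 4 = 76 h, and 76/24 = 3.17 days. The ±1 h window gives 75 to 77 h, or 3.13 to 3.21 days.
- The endpoint starts at randomization, so any lag to first dose adds to this. A lag of 8 h would give 77 + 8 = 85 h = 3.54 days. That is an outer bound, because the 8 h limit in the protocol runs from consent, which comes before randomization.
- If the patient waits for the scheduled Day 5 CECT (protocol 8.6, from 96 h): 96/24 = 4.0 days or more.
- Supportive care: no minimum, because the scan can be brought forward to an earlier discharge.

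**Effect on the mean.** Assumptions, none of them from the documents: time to readiness X is log-normal with the same distribution in both arms, the geometric SD is 1.6 to 2.0, the hold is followed by everyone, and there is no drug effect. With median m, σ = ln(geometric SD), minimum f and d = ln(f/m)/σ:

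- share held past readiness = Φ(d)
- days added to the mean = E[max(X, f)] − E[X] = f·Φ(d) − m·exp(σ²/2)·Φ(d − σ)

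Example with m = 3, geometric SD 1.6 (σ = 0.470) and f = 3.167: d = ln(1.0556)/0.470 = 0.115; Φ(d) = 0.546; the mean of X is 3 × exp(0.110) = 3.350; Φ(0.115 − 0.470) = 0.361. Days added = 3.167 × 0.546 − 3.350 × 0.361 ≈ 0.52.

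| Median readiness (days) | Days added, dosing hold (3.17 d) | Share held | Days added, Day 5 scan (4.0 d) | Share held |
|---|---|---|---|---|
| 3 | 0.52–0.65 | 53–55% | 1.05–1.15 | 66–73% |
| 4 | 0.23–0.39 | 31–37% | 0.57–0.76 | 50% |
| 5 | 0.11–0.25 | 17–26% | 0.31–0.51 | 32–37% |
| 8 | 0.01–0.07 | 2–9% | 0.05–0.17 | 7–16% |

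The median moves less. At a median readiness of 4 days or more, the drug-arm median does not change under either minimum. At 3 days it rises by about 0.17 (to 3.17) or 1.0 (to 4.0).

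**Masking of a true benefit.** Suppose the drug cuts every stay by 20%, the control median is 4 days and the log-SD is 0.5 to 0.7. The control mean is 4.53 to 5.11 days, so the true difference is −0.2 × 4.53 = −0.91 to −0.2 × 5.11 = −1.02 days. With a 3.17-day minimum the observed difference is −0.43 to −0.44 days. With a 4.0-day minimum it is +0.04 to +0.05 days.

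**The case against.** Several points on the other side stand.

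- *The scan is not an arm-specific hold.* The CECT is required in both arms, and protocol 8.11.14 lets it be brought forward for a planned early discharge without limiting this to one arm. A reader might infer from 5.2 a firm four-day minimum for drug patients. The text does not support that: a drug patient who finishes the fourth infusion at about 76 h can be scanned and leave on Day 4. The 4.0-day column applies only to patients who wait for the scheduled scan.
- *The hold is soft.* It is worded as *should*, and earlier discharge is open after contact with the Medical Monitor. Protocol 6.2 lets patients stop dosing at any time and reserves discontinuation for those who remain in hospital, so leaving before the fourth dose is foreseen. It would be too strong to say that the endpoint cannot show a benefit below the minimum. The figures above assume full adherence and are upper bounds in that respect.
- *The size depends on stays that the documents do not report.* At a median of 8 days the dosing effect is under 0.1 day.
- *The consequence is limited.* The endpoint is one of many secondary ones, untested, in a study that protocol 10.1 says is not powered for inference. The standard error of the arm difference is SD × √(1/18 + 1/6) = 0.471 × SD. The assumed distributions at medians of 3 to 5 days, with stays capped at 30 days, have an SD of about 1.7 to 4.7 days. The standard error is therefore 0.8 to 2.2 days, larger than the dosing shift in each case.
- *The direction is conservative.* The hold cannot create a false benefit. A reader might also infer that the dose-response comparison is distorted. Both dose groups have the same four-dose schedule, so the hold does not favour either.

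These points reduce the weight of the concern but do not remove it. Imprecision is not a reason to leave a known, one-directional bias unlabelled, and softening the hold in one arm does not create one in the other.

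**Conclusion.** The concern holds in a limited form. Followed as written, SAP 7.14 compares a stay that includes a protocol-requested dosing period with one that does not. The arm-specific part is a soft minimum of about 3.2 days from first dose. Under full adherence and equal log-normal readiness, it adds about 0.5–0.65 days to the drug-arm mean at a median of 3 days, 0.2–0.4 at 4, 0.1–0.25 at 5 and under 0.1 at 8. Waiting for the Day 5 scan raises these to 1.05–1.15, 0.6–0.8, 0.3–0.5 and 0.05–0.2. The medians and spreads are assumptions.

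The bias is against the drug and concerns drug versus supportive care only. It calls for labelling and a supportive summary. It does not justify dropping total days, and it does not affect the primary safety objective.

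**What to change.** In SAP 7.14:

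1. Keep total days, but label it as including a protocol-requested stay in the drug arm, and state that it is not an unbiased drug-versus-control comparison.
2. Report the number of drug patients discharged on the day of the fourth dose or of the CECT.
3. Add a supportive between-arm summary: days in hospital from 120 h after randomization to Day 30, counted as 0 for patients discharged alive earlier. State the rule for deaths before Day 30, for example assigning the maximum or listing them separately.

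The cost is SAP wording, one count and one derived variable from data already collected.

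The supportive summary has limits, which is why it should not replace total days. Differences in stay before Day 5 drop out. Under the same assumptions, 77–86% of patients would score zero at a median readiness of 3 days and 63–68% at 4 days (the share with X below 5 days). A CECT delayed to Day 6 or 7 leaves a small residual hold. No change to the discharge rule is proposed.

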For all 4 cohorts, a study physician or appropriately trained delegate will perform all assessments daily through Day 10, or until discharge if occurring earlier. After Day 10, and starting on Day 12, serious adverse events (SAEs) will be captured every 48 hours until Day 30 ( $\pm$  2 days), or until discharge if occurring earlier. Patients discharged prior to Day 30 will be contacted on Day 30 ( $\pm$  2 days) to capture SAEs and any re-admissions to the hospital. Patients will also be contacted on Day 90 ( $\pm$  7 days) to assess mortality.

CalciMedica may submit amendments to the protocol to modify the planned doses, the dosing schedule, the infusion time, the number of sites in the study, the total number of patients randomized in the study, the number of patients randomized in each cohort, the number of cohorts in each phase of the study, and/or the number of phases in the study for safety and/or efficacy considerations.

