**If the patient is discharged after Day 5 and before Day 10, Day 10 procedures should be performed prior to discharge.**

## 8.9 Days 12 – 30

For all patients who remain hospitalized:

- Perform AE/SAE assessment if the patient is in the hospital every 48 hours starting on Day 12 until discharge, or until Day 30

- If the patient has been discharged from the hospital, contact the patient on Day 30 ( $\pm 2$  days) for SAE assessment and to determine if patient has been readmitted to the hospital (may be conducted by phone call to patient, LAR, primary MD, or chart review)

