### 9.2 Definition of Serious Adverse Event

A serious adverse event (SAE) is any AE occurring at any dose and regardless of causality that:

- Results in death
- Is life-threatening
- Requires hospitalization or prolongation of existing hospitalization
- Results in persistent or significant incapacity or substantial disruption of the ability to conduct normal life function
- Is a congenital anomaly or birth defect in an offspring of a patient receiving CM4620-IE
- Is an important medical event

The term “life-threatening” refers to an event in which the patient was at immediate risk of death at the time of the event. It does not refer to an event that hypothetically might have caused death if it were more severe.

Important medical events are those that may not need any of the criteria defined above; however, they may be considered serious when, based upon appropriate medical judgment, they may jeopardize the patient and may require medical or surgical intervention to prevent one of the other outcomes listed in the SAE definition.

Pregnancy is not considered an AE; however, information will be collected for any pregnancies that occur during CM4620-IE administration or the thirty days thereafter. Certain pregnancy outcomes will require submission as an SAE.

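### Hospital and ICU time are each computed from a single stay, with no rule for the readmissions collected at Day 30; the resulting error can differ by arm

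*SAP*

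**What the plan says.** SAP 3.1.4 lists the number of hospitalized days as a secondary efficacy endpoint, split into total days and days in intensive care.

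SAP 7.14.1 gives the formulas.
- Hospital: "Total time in hospital is defined as (datetime of discharge from hospital", less the datetime of randomization.
- ICU: "The time in intensive care unit will be calculated as time of first ICU visit until discharge from ICU unit".
- Two special cases are covered. One is a missing end date: "If no endpoint is recorded, time in hospital/ICU will be set to 30 days". The other is death in hospital or ICU, where the date of death closes the interval.
- Readmission and repeat ICU stays are not mentioned.

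Readmissions are nevertheless sought. Protocol 3.1 contacts patients discharged before Day 30 "to capture SAEs and any re-admissions to the hospital", and SAP 3.2 repeats this. Protocol 8.9 describes the contact as "for SAE assessment and to determine if patient has been readmitted to the hospital".

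On leaving hospital, the arms are treated differently.
- Protocol 5.2: "The patient randomized to receive CM4620-IE should remain in the hospital until all 4 doses of CM4620-IE have been administered", and a CECT has been done. The investigator should contact the Medical Monitor before any earlier discharge.
- Protocol 8.6 foresees earlier discharge in the other arm: "If the PI wishes to discharge a patient randomized to supportive care only before Day 5", a CECT should come first.

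**The concern.** An endpoint labelled as total days is computed from one interval. A patient who goes home, relapses and returns has used more hospital days than the formula records. A poor course then looks like a good one, on an endpoint where fewer days is the better result.

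The arms may not be affected equally. CM4620-IE patients are expected to stay through four infusions and a CECT. Supportive-care patients have no dosing schedule to complete, and the protocol provides for their discharge before Day 5. Very short index stays, which a later return would contradict most sharply, are therefore easier to reach in the supportive-care arm. With few patients there, a single uncounted readmission has a visible effect on that arm's mean.

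**Working it through.** **Arm sizes.** Protocol 3.1 gives cohorts of 4, 4, 8 and 8, each randomized 3:1. The total is 4 + 4 + 8 + 8 = 24, which matches the stated sample size. CM4620-IE: 3 + 3 + 6 + 6 = 18. Supportive care: 1 + 1 + 2 + 2 = 6.

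**Expected minimum stay on CM4620-IE.** The fourth infusion starts 72 h (± 1 h) after the first and lasts 4 h (protocol 7.4, 8.5). It ends at 72 + 4 = 76 h (75 to 77 h), or 76/24 = 3.2 days. The Day 5 visit, with its CECT, begins at 96 h = 4.0 days. Protocol 5.2 therefore implies a stay of roughly 3.2 to 4 days or more, unless the patient is discharged earlier after contact with the Medical Monitor. Supportive care has no matching dosing requirement.

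**What each reading of the formula gives.** Take an invented patient discharged at day 3, readmitted at day 6 and discharged again at day 12.

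| Rule | Days recorded |
|---|---|
| First discharge minus randomization | 3 |
| Last discharge minus randomization | 12 (includes 6 − 3 = 3 days at home) |
| Sum over stays | 3 + (12 − 6) = 9 |

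Neither single-discharge reading gives the days actually spent in hospital. The same holds for two ICU stays separated by time on a ward.

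**Effect of one omitted readmission on an arm mean.** The shift is L/n, where L is the readmission length in days. The documents give no length, so L = 3 to 10 is assumed.

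| L (days) | Supportive care, L/6 | CM4620-IE, L/18 |
|---|---|---|
| 3 | 0.50 | 0.17 |
| 5 | 0.83 | 0.28 |
| 7 | 1.17 | 0.39 |
| 10 | 1.67 | 0.56 |

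Per event, the supportive-care mean moves 18/6 = 3 times as far.

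**The median is not immune.** With six invented supportive-care stays of 3, 5, 5, 6, 7 and 8 days, the mean is 34/6 = 5.67 and the median 5.5. If the 3-day patient is the one above, with 9 true days, the mean is 40/6 = 6.67 and the median 6.5.

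**Effect on the difference between arms.** The distortion is L × (p_control − p_treated), where p is the readmission rate. With L = 5, all rates being assumptions:
- equal rates: 0 days;
- 10% treated, 20% control: 5 × 0.10 = 0.5 day;
- 10% treated, 30% control: 5 × 0.20 = 1.0 day.

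In the last two cases supportive-care stay is understated relative to CM4620-IE. If the treated arm had the higher rate, the sign would change.

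**Where the readmissions would fall by count.** With a control-to-treated rate ratio r, the control share is 6r/(6r + 18). This is 25% at r = 1, 40% at r = 2, 50% at r = 3 and 57% at r = 4.

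**The case against.** **The SAP does not say which discharge it means.** This is correct: using the first discharge is the natural reading, not a stated rule. It does not rescue the definition, because a later discharge counts days at home.

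**Readmissions are not hidden.** SAP 4.5 says that in general all collected data are summarized and listed. A readmission caused by an adverse event also meets a seriousness criterion ("Requires hospitalization or prolongation of existing hospitalization", protocol 9.2) and would enter the adverse event tables. This stands in part: a reader could find the events. The hospital-day summary would still be wrong for those patients, and no readmission table by arm is specified.

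**Early discharge is not premature discharge.** The suggested discharge criteria in protocol 5.2 cover pain, diet and infection, and are not arm-specific. This stands, and it limits what can be said about direction.

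**The endpoint carries little weight.** It is one of many secondary endpoints, is summarized without a test, and belongs to a study not powered for inference. This limits the seriousness but does not remove the defect.

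**Summing stays has its own weaknesses.** Planned elective admissions would count as hospital burden, and an early in-hospital death would still score as a short stay. The first can be met with a flag. The second is a separate matter that this change does not solve.

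**Conclusion.** The point holds as a defect of definition. SAP 7.14.1 has no rule for a second admission or a second ICU stay, although the endpoint is labelled as total days and the plan sets out to find readmissions. One omitted readmission of an assumed 3 to 10 days lowers the supportive-care mean by 0.50 to 1.67 days, or the CM4620-IE mean by 0.17 to 0.56 days. This assumes full cohorts and the first-discharge reading. The endpoint is secondary and descriptive, so the change is worth making but does not bear on the primary safety objective.

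Three stronger conclusions that a reader might infer are not supported.
- *That the miscounted readmissions would be mostly in the supportive-care arm.* By count this needs a readmission rate more than three times that on CM4620-IE, and the documents give no rate for either arm. They support only that the error can differ by arm.
- *That only supportive-care patients can leave early.* Protocol 5.2 provides for earlier discharge on CM4620-IE after contact with the Medical Monitor. Protocol 8.6 asks for a CECT before early supportive-care discharge, and 8.11.14 asks for one before any discharge planned sooner than Day 5.
- *That the comparison would be reversed.* Neither document gives a length of stay by arm, so a reversal cannot be shown.

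**What to change.** In SAP 7.14.1:
- define hospital days as the sum of days over all admissions from randomization through Day 30, and ICU days as the sum over all ICU stays in the same window. The existing 30-day default already points to this horizon;
- keep the index stay (randomization to first discharge) as a separate row, named as such;
- add a table of 30-day readmission, number and percent, by arm;
- flag planned elective admissions so that totals can be shown with and without them.

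In data collection, record readmission and re-discharge dates at the existing Day 30 contact. As protocol 8.9 is worded, that contact establishes only whether a readmission occurred. The adverse event record in protocol 9.4 holds event onset and resolution dates, which may not be admission and discharge dates.

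The cost is revised SAP wording, a few date fields and slightly more programming. No new patient contact is needed.

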4.8 Handling of Drop-outs, Missing Data and Outliers

Outliers will be included in summary tables and listings, and will not be handled separately in any analyses. No imputation of missing data will be performed (however, will data entered in unscheduled visit be placed to the nearest applicable visit with missing values).

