7.1.3 Presentation

The adverse events will be present using frequency tables.

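### SAP 7.14.1 scores any hospital or ICU stay with no recorded end as 30 days, which is too long for ICU stays that start late and arbitrary for stays whose end is simply unknown

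*SAP*

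**What the plan says.** SAP 3.1.4 lists "Number of hospitalized days" as a secondary endpoint, split into total days and days in intensive care. SAP 7.14.1 measures hospital time from randomization to discharge. ICU time has a different origin: "The time in intensive care unit will be calculated as time of first ICU visit until discharge from ICU unit". Two rules cover stays without an ordinary discharge. For a missing end: "If no endpoint is recorded, time in hospital/ICU will be set to 30 days". For death: "If the patient died in hospital/ICU, the date of death (time 00:00 imputed if missing) will be used to calculate time in hospital/ICU".

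SAP 7.14.2 plans no test. SAP 7.14.3 says: "Both the total number of hospital days and number of days at ICU will be presented using summary statistics". The general missing-data rule in SAP 4.8 says: "No imputation of missing data will be performed". The only qualification there concerns moving unscheduled-visit data to a nearby visit.

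On follow-up, Protocol 3.1 and 8.9 have inpatients assessed every 48 hours from Day 12 to Day 30 or discharge. Patients already discharged are contacted on Day 30 (±2 days) about SAEs and re-admission.

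**The concern.** The 30-day rule does not ask why the end is missing. A patient still in hospital at Day 30, a patient whose discharge date was lost and a patient who withdrew consent all receive the same value. Only the first is known to have stayed that long.

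The rule also gives one number to two durations with different starting points. For hospital time, 30 days coincides with Day 30. For ICU time it does so only if ICU entry was at randomization. With later entry the value runs past Day 30. It can also exceed the patient's own hospital time, for example when hospital discharge is recorded before Day 30 but ICU discharge is not.

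At stake are the means and standard deviations of a descriptive endpoint in small groups, where one assigned value can change how the arms compare.

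**Working it through.** **Group sizes.** Cohorts of 4, 4, 8 and 8 (Protocol 3.1) sum to 24, which reproduces the total in Protocol 10.1 and SAP 3.3. At 3:1 the drug arm has 3 + 3 + 6 + 6 = 18 patients and the control arm 1 + 1 + 2 + 2 = 6.

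**Hospital time, patient in hospital at Day 30.** In Protocol section 8, Day *k* starts at 24 × (*k* − 1) hours (Day 5 at 96 h, Day 10 at 216 h). Day 30 therefore runs from 696 to 720 h, or 29 to 30 days after randomization. A value of 30 is right to within a day.

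**ICU time, patient still in ICU at Day 30.** Days available = (696 or 720 − entry hour) / 24.

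| ICU entry at start of | Entry hour | Days available | Value assigned | Excess |
|---|---|---|---|---|
| Day 5 | 96 | 25–26 | 30 | 4–5 |
| Day 10 | 216 | 20–21 | 30 | 9–10 |
| Day 20 | 456 | 10–11 | 30 | 19–20 |

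One such patient with Day 10 entry raises the mean ICU time by 9/6 to 10/6 = 1.50 to 1.67 days in the control arm, or 9/18 to 10/18 = 0.50 to 0.56 days in the drug arm. No assumption about length of stay is needed beyond the ICU stay lasting to Day 30.

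**End unknown for another reason.** If the true stay is *t* days, scoring it as 30 moves a group mean by (30 − *t*)/*n*. The documents give no length of stay, so *t* is an assumption, shown over a range.

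| True stay *t* | 6 controls | 18 drug patients |
|---|---|---|
| 3 days | 27/6 = 4.50 | 27/18 = 1.50 |
| 7 days | 23/6 = 3.83 | 23/18 = 1.28 |
| 21 days | 9/6 = 1.50 | 9/18 = 0.50 |

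For the 12 second-phase drug patients with *t* = 7, the shift is 23/12 = 1.92 days. The median is less affected. With assumed stays of 5, 6, 7, 7, 8 and 9 days, changing one 7 to 30 moves the mean from 7.0 to 10.8 and the SD from 1.4 to 9.5, but the median only from 7.0 to 7.5.

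**Death.** Five assumed stays of 5, 6, 7, 8 and 9 days have mean 35/5 = 7.0. A sixth patient who dies at 2 days gives 37/6 = 6.2; one who dies at 14 days gives 49/6 = 8.2. The mean stay cannot be read without knowing how many patients died.

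**The case against.** The best defence is that in-hospital follow-up stops at Day 30, so the 30 days is administrative truncation rather than imputation, and that a specific endpoint rule overrides the general one in SAP 4.8. For hospital time in a patient known to be present at Day 30, that stands. It does not rescue the ICU value, which is not a truncation at Day 30 unless ICU entry was at randomization. It does not cover a lost discharge date either. The SAP nowhere says that 7.14.1 overrides 4.8, although a cross-reference would settle that.

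It is also fair that unknown ends should be rare. Assessments are daily to Day 10 and every 48 hours from Day 12, with a Day 30 contact after discharge. The eCRF, which is not in the documents, may hold a status field, but the SAP rule does not call on one. The summary under SAP 4.5 includes median, minimum and maximum, with listings, so a reader could spot a value of 30. That helps in tracing the case but leaves the mean and SD as they are. The threefold difference in shift between arms is simply 18 against 6 and would apply to any endpoint.

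A reader might infer more than the documents support:

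- **ICU time has no starting point.** It has one, the first ICU visit. Only the substituted 30 days lacks an anchor.
- **Patients never in ICU score 30.** ICU time is defined from a first ICU visit, so without a visit there is no stay to end. The SAP should state 0, but the literal reading is strained.
- **Ending the stay at death is an error.** It is a valid count of days in hospital. SAP 7.13.1 has the incidence of death calculated, and 7.13.3 says: "The incidence of death will be presented using listings". Fatal adverse events also enter the tables under 7.1.3: "The adverse events will be present using frequency tables". What is missing is a count beside the stay summary.
- **The request in Protocol 5.2 that drug patients stay through dosing biases the comparison.** Its size cannot be derived, because the documents say nothing about when patients would be ready to leave.

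**Conclusion.** The point holds, at minor severity. As written, the rule gives a wrong value for an ICU stay that begins after randomization and is still open at Day 30: 4 to 5 days too many for entry at the start of Day 5, and 19 to 20 for Day 20. It gives an arbitrary value when the end is unknown for reasons unrelated to still being in hospital. In the 7-day illustration that costs 3.83 days on the control mean and 1.28 on the overall drug mean.

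The ICU result rests only on the SAP's definitions and the protocol's day numbering. The second result rests on an assumed true stay and on at least one such patient occurring, which follow-up makes unlikely but does not exclude. No test, error rate or sample size is affected; the consequence is confined to descriptive summaries by arm.

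**What to change.** In SAP 7.14.1:

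- Truncate hospital and ICU time at Day 30 (720 h) from randomization, so that an ICU stay ongoing at Day 30 counts from ICU entry to Day 30.
- Apply the Day 30 value only to patients confirmed in hospital or ICU at the existing Day 30 check.
- Treat every other unknown end as missing, report the number by arm, and cross-refer to SAP 4.8 so that the two sections agree.
- State 0 ICU days for patients never in ICU.

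In SAP 7.14.3, show the number of deaths by arm with the stay summary. A supportive summary of days alive and out of hospital is optional.

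The cost is SAP wording and a short derivation, with no new visit. There are two downsides. Patients with unknown ends leave the mean, which matters in a six-patient arm and is why their count must be shown. The ICU dates and the status at Day 30 must also be confirmed as captured on the eCRF: the schedule of events in Protocol Appendix 11 has no ICU item, and the Day 30 contact carries a ±2-day window.
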